#### **8.4.3      Pregnancy and assessments of fertility**

All pre-menopausal women who are not surgically sterile will have pregnancy testing.

**Serum pregnancy tests** will be performed at Screening and End of Treatment (End of Treatment visit/week 12 being the first visit of the open-label treatment period in case the subject agrees to participate).

**Urine pregnancy tests** will be performed at the remaining double-blind treatment visits, every three months during the open-label treatment period and at the End of Treatment Open-Label visit. Kits will be provided by the Central Lab only for the double-blind treatment visits assessments.

The specific schedule is outlined in [Table 8-1](#).

For more details about potential deviation in case of local regulations, please refer to [Section 5.2](#) and Exclusion criterion #22.

**During COVID-19 pandemic**, if a subject cannot visit the site to have pregnancy tests conducted the subject may complete a urine pregnancy test at home and report the result to the site. It is important that subjects are instructed to perform the urine pregnancy test first and only if the test result is negative proceed with the administration of the study treatment. A communication process should be established with the subject so that the site is informed of the pregnancy test results.

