- **Safety follow-up (8 weeks):** in subjects completing the double-blind treatment period, but not entering into the open-label treatment period, a safety follow-up visit will occur 8 weeks after the Week 12 visit (Week 20). Subjects who discontinue study drug during the double-blind treatment period and who do not remain in the study to follow the assessment schedule until the Week 12 FUP visit, will have the safety follow-up visit 12 weeks after the last dose. For subjects discontinuing double-blind treatment and remaining in the study to follow the assessment schedule until the Week 12 FUP visit, the Safety Follow-Up visit should occur on Week 20 even if the last dose was taken at Day 1. The Safety Follow-Up visit is not required in subjects who discontinue or complete the open-label treatment period.
- **Open-label treatment (until launch of erenumab in the country or until June 2021 in Korea):** all subjects completing the double-blind treatment period on study drug are invited to participate. Eligible subjects who consented to participate in this open-label treatment period will receive erenumab until it is launched in the country, or until June 2021 in Korea, in order to ensure continued drug access.

Should a treatment gap exist between the two treatment periods due to a delay of HA/EC approvals or other administrative/logistical reasons, the subject may enter the open-label treatment period at a later time provided he or she still meets the eligibility criteria. During this treatment gap, the subject is allowed to use standard of care.

See the assessment schedule in [Table 8-1](#).

Two interim analyses (IA) are planned for this study:

- A **blinded IA**, after approximately 50% (275) of subjects have completed the double-blind treatment period (including early withdrawals), will be conducted to re-estimate the sample size by providing information on the variance for this trial relative to the planned assumptions to account for potential higher variability in general Asian population.

- An **unblinded IA** will be conducted after 70% (385, if no increase of sample size is needed following the blinded IA) of subjects have completed the double-blind treatment period (including early withdrawals), to determine whether the study will stop early or continue to the final primary analysis (full sample size). Study recruitment will continue until unblinded IA read-out.

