  - Total bilirubin (TBIL)  $\geq 2.0 \times$  upper limit of normal (ULN) or alanine transaminase (ALT) or aspartate aminotransferase (AST)  $\geq 3.0 \times$  ULN, as assessed by the central laboratory at initial screening
  - Known history of acute/active hepatitis B virus (HBV) or hepatitis C virus (HCV) within 3 months prior to screening according to local clinical practice
17. Myocardial infarction (MI), stroke, transient ischemic attach (TIA), unstable angina, or coronary artery bypass surgery or other revascularization procedure within 12 months prior to screening
18. Subject has any clinically significant vital sign, laboratory, or electrocardiogram (ECG) abnormality during screening that, in the opinion of the investigator, could pose a risk to subject safety or interfere with the study evaluation
19. Score “yes” on item 4 or item 5 of the Suicidal Ideation section of the Columbia Suicide Severity Rating Scale (C-SSRS), if this ideation occurred in the past 6 months, or “yes” on any item of the Suicidal Behavior section, except for the “Non-Suicidal Self-Injurious Behavior” (item also included in the Suicidal Behavior section), if this behavior occurred in the past 2 years.
20. Evidence of drug or alcohol abuse or dependence within 12 months prior to screening, based on medical records, patient self-report, or positive urine drug test performed during screening (with the exception of prescribed medications such as opioids or barbiturates)
21. Pregnant or nursing (lactating) women
22. Women of childbearing potential, defined as all women physiologically capable of becoming pregnant, unless they are using basic methods of contraception during dosing of investigational drug. Basic contraception methods include:
  - Total abstinence (when this is in line with the preferred and usual lifestyle of the subject. Periodic abstinence (eg, calendar, ovulation, symptothermal, post-ovulation methods) and withdrawal are not acceptable methods of contraception
  - Female sterilization (have had surgical bilateral oophorectomy with or without hysterectomy), total hysterectomy or tubal ligation at least six weeks before taking investigational drug. In case of oophorectomy alone, only when the reproductive status of the woman has been confirmed by follow up hormone level assessment
  - Male sterilization (at least 6 m prior to screening). For female subjects on the study, the vasectomized male partner should be the sole partner for that subject

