**Table 8-1 Assessment Schedule**

Period	Screening		Double-Blind Treatment 				Post Double-Blind Treatment Follow-Up 				Open-Label Treatment 					
	Visit Name	Screening	Baseline	Day 1	Week 4	Week 8	End of Treatment (EOT)	Week 4 FUP 	Week 8 FUP 	Week 12 FUP 	Safety Follow -Up 	Week 12	Week 16, 20, 28, 32, 40, 44...	Week 24	Week 36, 48, and every 12 weeks	End of treatment Open-label
Days	-42	-28	Day 1	28	56	84		28	56	84	140	84	112, 140, 196, 224, 280, 308...	168	252, 336...	
Weeks	-6	-4	1	4	8	12		4	8	12	20	12	16, 20, 28, 32, 40, 44...	24	36, 48...	
Vital signs and body measurements 	X	X	X	X	X	X		X	X	X	X					
Chemistry	X		X				X				X			X		
Hematology	X		X				X				X			X		
Pregnancy Test (serum)	X						X									
Pregnancy test (urine)		S	S	S	S			S	S	S	S			S	S	S
Urine Drug Screen	X															
Anti-AMG 334 antibodies 			X				X				X					
eDiary Dispensing		S														
eDiary Return 			S	S	S	S		S	S	S						
Clinical Outcome Assessment(s)			X 					X 								

Period	Screening		Double-Blind Treatment 				Post Double-Blind Treatment Follow-Up 				Open-Label Treatment 					
	Visit Name	Screening	Baseline	Day 1	Week 4	Week 8	End of Treatment (EOT)	Week 4 FUP 	Week 8 FUP 	Week 12 FUP 	Safety Follow-Up 	Week 12	Week 16, 20, 28, 32, 40, 44...	Week 24	Week 36, 48, and every 12 weeks	End of treatment Open-label
Days	-42	-28	Day 1	28	56	84		28	56	84	140	84	112, 140, 196, 224, 280, 308...	168	252, 336...	
Weeks	-6	-4	1	4	8	12		4	8	12	20	12	16, 20, 28, 32, 40, 44...	24	36, 48...	
Concomitant medications	X	X	X	X	X	X	X	X	X	X			X	X	X	X
Concomitant therapies	X	X	X	X	X	X	X	X	X	X			X	X	X	X
Adverse Events 	X	X	X	X	X	X	X	X	X	X						
Study drug administration 			X	X	X							X	X	X	X	
Study Disposition Form						X					X					X

X Assessment to be recorded in the clinical database or received electronically from a vendor

S Assessment to be recorded in the source documentation only

 All study visit target dates are to be calculated from the Day 1 visit date, and all study procedures for a given visit should be completed in the same day.

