#### 8.4.1 Laboratory evaluations

A central laboratory will be used for analysis of all specimens collected. Central lab will provide urine pregnancy test to be assessed at site during the double-blind treatment period. Site will have to use local pregnancy test during the open-label treatment period. Details on the collections, shipment of samples and reporting of results by the central laboratory are provided to investigators in the laboratory manual.

Clinically notable laboratory findings are defined in [Section 16.1](#)

During the **COVID-19 pandemic** that limits or prevents on-site study visits, or if visits by site staff to a subject's home are not feasible, the collection of samples may be modified by Novartis and will be communicated to the investigator (e.g., local lab collection of samples).

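### No pregnancy test is required for open-label entry after a treatment gap, and on-time entrants need no result before their first open-label dose

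*Protocol*

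**What the plan says.** **Double-blind period.** Table 8-1 marks a urine test at Baseline, Day 1, Week 4 and Week 8. Section 8.4.1 says: "Central lab will provide urine pregnancy test to be assessed at site during the double-blind treatment period".

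**Moving into the open-label period.** Section 8.4.3 places serum tests at Screening and End of Treatment, the "End of Treatment visit/week 12 being the first visit of the open-label treatment period in case the subject agrees to participate". On analysis, 8.4.1 says: "A central laboratory will be used for analysis of all specimens collected". It leaves the details of result reporting to the laboratory manual. SAP 2.1 (note to Table 2-1) foresees that the End of Treatment visit and the first open-label injection can share a date.

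**Open-label period.** The open-label Week 12 column of Table 8-1 marks a dose but no serum or urine test. Urine tests are marked at Week 24, at Weeks 36 and 48 and every 12 weeks after that, and at the end of open-label treatment. The kit is local: "Site will have to use local pregnancy test during the open-label treatment period".

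**Treatment gap.** If approvals or logistics delay the open-label period, Section 3 says "the subject may enter the open-label treatment period at a later time provided he or she still meets the eligibility criteria". It gives no maximum length and names no test.

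**Test-then-dose order.** Section 8.4.3 writes this order once, in its COVID-19 paragraph, for subjects who cannot come to the site. They are to "perform the urine pregnancy test first and only if the test result is negative proceed with the administration of the study treatment".

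**Section 4.5** states that women of childbearing potential are tested at every study visit.

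**The concern.** Section 4.5 treats fetal exposure as a risk because CGRP may matter for fetoplacental development and fetal survival. Section 10.1.4 requires treatment to stop on pregnancy. The first open-label dose is the first erenumab exposure for everyone who had been on placebo, so it resembles Day 1 for them, yet it has less same-visit testing than Day 1.

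The late entrant is the weaker-protected case. She has been off study drug for an unspecified time and must still be eligible, but the schedule produces no new pregnancy result to support that check. The contraception requirement in exclusion criterion 22 is tied to dosing of the investigational drug, so it does not clearly cover an off-drug gap.

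**Working it through.** No statistical calculation applies. The check sets the dosing row of Table 8-1 against its two pregnancy-test rows, using the text of 8.4.3 and 8.4.1 to confirm them. The table is damaged in the available copy, but 8.4.3 independently confirms the End of Treatment serum test and the three-monthly open-label urine test.

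| Dose | Serum test that day | Urine test that day |
|---|---|---|
| Day 1, Week 4, Week 8 | none | yes, at each, read at site |
| First open-label dose, on time (End of Treatment/Week 12) | sample taken, analysed centrally | none |
| First open-label dose after a gap, by the open-label Week 12 column | none | none |
| Open-label Weeks 24, 36, 48 and every 12 weeks | none | yes, local kit |

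**On-time entry.** The last site-read test is at Week 8 and the dose is at Week 12: 12 − 8 = 4 weeks. A serum sample is taken on the day, so the woman is tested. What is missing is a rule that the result be known before the injection.

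**Entry after a gap.** Let g be the gap in weeks after Week 12. The documents do not give g, so the values below are assumptions for illustration.

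- Age of the End of Treatment serum test at the first open-label dose: g.
- Age of the last site-read test: (12 − 8) + g = 4 + g.
- With g = 4 (entry at Week 16): 4 and 8 weeks.
- With g = 20 (entry at Week 32): 20 and 24 weeks.

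Two features of Table 8-1 can shorten these intervals:

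- Note 4 requires a Safety Follow-Up visit for those who complete double-blind treatment without continuing. That visit, at Week 20, has a urine test. If it applies to a woman waiting out a gap, the last test at Week 32 is 32 − 20 = 12 weeks old rather than 20.
- Note 1 counts visit dates from Day 1. A woman entering at nominal Week 24, 36 or 48 (g = 12, 24 or 36) would meet a scheduled urine test that day.

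Both depend on circumstances or on how the table is read. Neither is a rule for the first open-label dose.

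**Eligibility on late entry.** Criterion 21 in Section 5.2 excludes "Pregnant or nursing (lactating) women". Section 5.3 presents the open-label criteria as additional ones, so criterion 21 can be read as still applying. Sections 3, 5.3 and 8.4.3 and Table 8-1 name no test with which to check it.

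**Section 4.5 against the schedule.** Section 8.4.3 and Table 8-1 agree with each other: open-label dosing is every 4 weeks and urine testing every 12. Only the sentence in 4.5 differs.

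**The case against.** The best reply is that on-time entry is already covered. A serum test is planned at the visit that doubles as the first open-label visit, and the sparse open-label Week 12 column may simply be one physical visit split over two columns, with the assessments listed under End of Treatment. That stands. A reader might infer that on-time entrants get no pregnancy test, and the documents contradict this. A reader might also infer that the serum result always arrives too late. The documents do not support that either, because reporting is left to the laboratory manual and no turnaround is stated. What remains is the absence of a result-before-dose rule.

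For late entry, the sponsor can point to the continued-eligibility condition, the contraception requirement, and Section 14, which lets investigators add safety assessments case by case. It can add that 8.4.1 tells sites to use local tests in the open-label period. These provisions permit a test before a late first dose. None requires one, and Table 8-1 marks none in the open-label Week 12 column.

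It would also be tempting to read the mismatch with Section 4.5 as showing that three-monthly open-label testing is itself deficient. The documents do not support that: 4.5 is benefit-risk narrative, and the operative text and table consistently set the three-monthly schedule.

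**Conclusion.** The point holds, as a minor one. For entry after a treatment gap, no pregnancy test is scheduled unless the date coincides with a visit that has one. For on-time entry, a same-day serum sample exists but its result need not be known before the injection, whereas each double-blind dose has a site-read test at the same visit.

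The size is one dosing occasion per woman of childbearing potential who enters the open-label period. The number of such women, the number with a gap and the length of the gap are not in the documents, so no risk of exposure is estimated. Earlier tests and required contraception limit the gap. The double-blind data, the primary analysis and the type I error are unaffected.

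The conclusion rests on reading Table 8-1 as confirmed by 8.4.3, and on the laboratory manual containing no result-before-dose rule. If the manual has one, the on-time part is met outside the protocol, and the late-entry part stands. The Section 4.5 mismatch is editorial only.

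**What to change.** 1. In 8.4.3 and the open-label Week 12 column of Table 8-1, require for women of childbearing potential a negative local urine pregnancy test on the day of, and before, the first open-label dose, whenever that dose occurs. Keep the End of Treatment serum sample. This carries the order already written for home dosing over to the on-site first open-label dose.
2. In Section 4.5, replace the statement of testing at every visit with 'according to the schedule in Table 8-1'. A pointer also covers the follow-up and End of Treatment Open-Label tests without listing them.

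The cost is one local urine kit per woman, of a kind that sites already use in this period, an occasional short delay to a first open-label dose, and one reworded sentence.

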#### **8.4.4      Prospective suicidality assessment**

The C-SSRS is a questionnaire that prospectively assesses Suicidal Ideation and Suicidal Behavior. The C-SSRS must be administered at each visit of the double-blind treatment period, including unscheduled visits.

A validated version of the electronic Columbia Suicide Severity Rating Scale eC-SSRS will be used to capture self-reported eC-SSRS data via a web-based interactive response system and via a phone system (both interchangeable). The eC-SSRS uses a detailed branched logic algorithm to perform the eC-SSRS subject interview, evaluating each subject's suicidality ideation and behavior in a consistent manner. At the conclusion of each assessment, a detailed eC-SSRS Findings Report will be available on the vendor portal. If the system assesses the subject as having positive suicidal signs, the investigator will be immediately notified by either email and via telephone.

If, at any time after screening and/or baseline, the score is “yes” on item 4 or item 5 of the Suicidal Ideation section of the C-SSRS or “yes” on any item of the Suicidal Behavior section, the subject must be referred to a mental health care professional for further assessment and/or treatment. The decision on whether the study treatment should be discontinued is to be taken by the investigator in consultation with the mental health professional to whom the subject is referred.

In addition, all life-threatening events must be reported as SAEs. For example, if a subject answers “yes” to one of the questions in the Suicidal Behavior section, an SAE must be reported if the event was life-threatening. All events of “Non-Suicidal Self-Injurious Behavior” (question also included in the Suicidal Behavior section) should be reported as AEs and assigned the appropriate severity grade.

All SAEs relating to suicidal behavior must be reviewed by the safety physician.

During the **COVID-19 pandemic** that limits or prevents on-site study visits, the eC-SSRS may still be collected via a web-based interactive response system or via a phone system (both interchangeable). In this latter case, the dialing number will be temporarily kept by the vendor.

#### **8.4.5 Appropriateness of safety measurements**

The safety assessments have been selected based upon the safety profile of the drug as reported in the Investigator Brochure, are standard for this subject population and drug class.

### **8.5 Additional assessments**

#### **8.5.1 Clinical Outcome Assessments (COAs)**

Clinical Outcome assessments (COAs) will be collected by subjects using a handheld electronic diary (eDiary) at various frequencies during the **double-blind treatment period**.

The eDiary will collect the following COAs daily, at home:

- Date and time of start of headache (i.e. migraine or non-migraine headache)
- Date and time of end of headache
- [REDACTED]
- Pain features (e.g. one-sided, throbbing, worsens with exercise/physical activity)
- Symptoms (e.g. aura, nausea, vomiting, photophobia, phonophobia)
- Use of acute headache medications (medication name [from pre-entered list], date of dosing, number of times taken of each date, number of units taken)

The eDiary will categorize headache events as migraine days or headache days based on the definitions below:

- Headache Day: Any calendar day in which the subject experiences a qualified migraine or a non-migraine headache (initial onset, continuation, or recurrence of the headache lasting  $\geq 4$  continuous hours, or a headache of any duration for which acute medication was administered for treatment of headache pain). A headache event that is lasting less than 24 consecutive hours in duration, regardless if it extends into the prior or next calendar day for less than 4 hours even if acute medication is taken on the prior or next calendar day, should be counted as a single headache day.

- Migraine Day: see [Section 8.3.1](#) for details.

The site study staff will train the subject on how to use the eDiary (e.g. turning on/off, charging, navigating screens, transmitting data, contacting the help desk for technical assistance) and complete the questions. The subject will be instructed to interact with the eDiary every day during the baseline period and treatment period and to bring the eDiary to every study visit. At the Day 1 study visit, the investigator will use the subject's eDiary device to review all data entered during the baseline period and confirm the relevant inclusion and exclusion criteria. Please refer to the eDiary manual for additional details.

During the COVID-19 pandemic that limits or prevents on-site study visits, COA information may still be collected using the eDiary.

### **8.5.2 Patient Reported Outcomes (PROs)**

The eDiary will collect the following patient-reported outcomes (PRO) until the end of the double-blind treatment period:

- mMIDAS, monthly
- [REDACTED]
- [REDACTED]
- Beck Depression Inventory, screen

For those PROs that are completed during the site visit, subjects must complete the PROs before any clinical assessments are performed.

Subject questionnaires as well as the COAs should be completed in the language most familiar to the subject. The subject should be given sufficient space and time to complete the PRO measure(s).

The responses (COAs and PROs) stored electronically in the database will be considered the source file.

Site staff will review eDiary compliance with the patient at each applicable visit.

#### **8.5.2.1 Modified Migraine Disability Assessment Questionnaire (mMIDAS)**

The modified MIDAS is a 5-item self-administered questionnaire that sums the number of productive days lost over the past month in two settings: the workplace and the home. The MIDAS also assesses disability in family, social, and leisure activities. The MIDAS score is the sum of missed days due to a headache from paid work, housework, and non-work (family, social, leisure) activities; and days at paid work or housework where productivity was reduced by at least half. The analysis will be based on total score, subscore of absenteeism (items 1, 3, and 5) and subscore of presenteeism (items 2 and 4).

Subjects will complete the MIDAS at the timepoints outlined in [Table 8-1](#). The recall period is the past one month. The questionnaire takes approximately 5 minutes to complete.

[figure not shown]

#### **8.5.2.4 Beck Depression Inventory (BDI)-II**

The BDI-II is a 21-item questionnaire that assesses severity of depression. Each item is scored from 0 to 3. The total score is categorized into 4 severity grades: minimal depression (0-13), mild depression (14-19), moderate depression (20-28), and severe depression (29-63).

Subjects will complete the BDI-II at the timepoint outlined in [Table 8-1](#). The recall period is the preceding two weeks, including the day of completion. The questionnaire takes approximately 10 minutes to complete.

